6.4.1.1 Incidence of Unsolicited Adverse Events

An overall summary of unsolicited TEAEs including the number and percentage of participants who experience the following within 28 days after vaccination (See [Section 6.2.6](#) for safety analysis periods) will be presented:

- Any unsolicited TEAEs (See [Section 6.2.6](#) for study periods)
- Any unsolicited serious TEAEs
- Any unsolicited fatal TEAEs
- Any unsolicited medically attended TEAEs
- Any unsolicited treatment-emergent AESI

- Any unsolicited TEAEs leading to discontinuation from participation in the study
- Any unsolicited severe TEAEs

The table will also include number and percentage of participants with unsolicited TEAEs within 28 days after vaccination that are treatment-related in each of the above categories.

In addition, separate listings containing individual participant AE data for unsolicited TEAEs, unsolicited TEAEs leading to withdrawal from study participation, unsolicited AESI, and unsolicited medically attended TEAEs will be provided. Unsolicited treatment-related TEAEs, unsolicited severe TEAEs, unsolicited treatment-related severe TEAEs, unsolicited serious treatment-related AEs, unsolicited treatment-related medically attended TEAEs, unsolicited adverse events leading to death, and unsolicited TEAEs for participants with influenza or SARS-CoV-2 infection will also be provided in corresponding listings.

6.4.1.2 TEAEs by System Organ Class and Preferred Term

The following summary tables of TEAEs will be provided by SOC and PT using frequency counts and percentages (i.e., number and percentage of participants with an event):

- All unsolicited TEAEs
- All unsolicited TEAEs that are treatment-related
- All unsolicited TEAEs leading to withdrawal from study participation
- All unsolicited severe TEAEs
- All unsolicited severe TEAEs that are treatment-related
- All unsolicited treatment-emergent AESIs
- All unsolicited medically attended TEAEs
- All unsolicited medically attended TEAEs that are treatment-related

6.4.1.3 TEAEs by Preferred Term

Summary tables of all unsolicited TEAEs within 28 days after vaccination will be provided by preferred term. PTs will be sorted in a descending order according to the frequency in total in each type of vaccination group.

6.4.1.4 TEAEs by System Organ Class, Preferred Term, and Severity

The following summary tables of TEAEs within 28 days after vaccination will be provided by SOC, PT, and maximum severity (mild, moderate, severe) using frequency counts and percentages:

- All unsolicited TEAEs
- All unsolicited TEAEs that are treatment-related

6.4.2 Serious Adverse Events

An AE (including an AR) is considered an SAE if, in the view of either the Investigator or Sponsor, it results in any of the following outcomes:

- Death
- Life-threatening
- Inpatient hospitalization or prolongation of existing hospitalization
- Persistent or significant incapacity or substantial disruption of the ability to conduct normal life functions
- Congenital anomaly or birth defect
- Medically important event

The overall summary of unsolicited TEAEs in Section 6.4.1.1 will include the following:

- Any unsolicited serious TEAEs
- Any unsolicited serious treatment-related TEAEs

The following summary tables of unsolicited serious TEAEs within 28 days and overall period will be provided by SOC and PT using frequency counts and percentages (i.e., number and percentage of participants with an event):

- All unsolicited serious TEAEs
- All unsolicited serious TEAEs that are treatment-related

6.4.3 Solicited Adverse Reactions

Solicited ARs refers to selected signs and symptoms occurring after vaccination during a specified post-vaccination follow-up period (day of vaccination and 6 subsequent days). The solicited ARs are recorded daily by the participant in the eDiary.

If a participant reported a solicited AR during the solicited period and did not record the event in the eDiary, the event should be recorded on the Reactogenicity page of the eCRF. If the event starts during the solicited period, but continues beyond 7 days after dosing, the participant should notify the site to provide an end date to close out the event on the Reactogenicity page of the eCRF. If the participant reported an event after the solicited period (i.e., after Day 7), it should be recorded as an AE on the AE page of the eCRF.

All solicited ARs (local and systemic) will be considered causally related to dosing or study vaccination.

Analyses of solicited ARs will be provided by vaccination group based on the Solicited Safety Set. All solicited ARs (overall, local, and systemic) reported during the 7-day follow-up period after vaccination will be summarized. A 2-sided 95% CI using the Clopper-Pearson method will also be provided for the percentage of participants with any solicited AR.

- The number and percentage of participants who reported solicited local ARs and solicited systemic ARs during the 7-day follow-up period after injection or persisting beyond 7 days after injection will be tabulated by vaccination group and toxicity grade.
- The number and percentage of participants who reported each individual solicited AR will also be summarized by vaccination group, toxicity grade, and day of reporting based on the eDiary. Analyses will be displayed for each age group.

A two-sided 95% CI using the Clopper-Pearson method will be provided for the percentage of participants who reported any solicited AR, any solicited local AR, or any solicited systemic AR.

The onset of individual solicited ARs is defined as the time point after injection at which the respective solicited AR first occurred. The number and percentage of participants with onset of individual solicited AR within 7 days will be summarized by vaccination group and onset day relative to injection day (Day 1). Analyses will be displayed for each age group.

The number of days reporting each solicited AR will be summarized descriptively and categorically for the following time windows (1-2 days, 3-4 days, 5-6 days, and 7 days) by vaccination group (and then by age group).

The number of days will be calculated as the day(s) the solicited AR is reported within 7 days of injection including the day of injection, no matter if it is intermittent or continued.

Solicited local, solicited systemic ARs and solicited ARs persisting beyond 7 days collected in the eDiary will be provided in corresponding listings, and the maximum toxicity grade from eDiary will be presented. Severity grading of reactogenicity will occur automatically based on participant entry into the eDiary according to the grading scales presented in Table 7 of the protocol Section 8.4.3. modified from the Toxicity Grading Scale for Healthy Adult and Adolescent Volunteers Enrolled in Preventive Vaccine Clinical Trials (DHHS 2007b).

6.4.4 Clinical Laboratory Evaluations

Safety laboratory testing will include hematology and serum chemistry.

For continuous hematology and serum chemistry parameters, the observed values and changes from baseline will be summarized at each time point by vaccination group and then by age group as defined in [Section 6.2.9](#).

Summary of Grade 3+ laboratory abnormalities by visit and toxicity grades will be provided by vaccination group and then by age group as defined in [Section 6.2.9](#).

Hematology and chemistry toxicity grades will be summarized using a shift table from baseline to Day 8 by vaccination group.

All laboratory test results will be presented in the data listings. The results that are outside the reference ranges will be flagged in the data listings. The abnormalities meeting the toxicity grading criteria (Grade 3 or higher) in [Appendix E](#) in any safety laboratory (hematology and serum chemistry) will be listed separately.

A pregnancy test will be performed on all female participants of childbearing potential at the Screening Visit and before vaccine administration on Day 1 via point-of-care urine, and as needed at unscheduled visits (urine or blood pregnancy test based on the investigator's discretion).

The pregnancy test results will be listed.

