Demographic variables (eg., age, gender, race, ethnicity, height, weight, and body mass index) and baseline characteristics will be summarized by vaccination group and overall. Summary

For the FAS, participants will be analyzed according to the group to which they were randomized.

The PP Set will be used as the primary analysis set for analyses of immunogenicity unless otherwise specified. Participants will be analyzed according to the group to which they were randomized.

The Safety Set will be used for all analyses of safety, except for the solicited ARs. Participants will be included in the vaccination group corresponding to what they actually received.

The Solicited Safety Set will be used for the analyses of solicited ARs and participants will be included in the vaccination group corresponding to what they actually received.

statistics (mean and standard deviation for continuous variables, and number and percentage for categorical variables) will be provided.

9.5.2. **Safety Analyses**

All safety analyses will be based on the Safety Set, except summaries of solicited ARs, which will be based on the Solicited Safety Set. All safety analyses will be provided by vaccination group. Participants will be included in the vaccination group corresponding to what they actually received.

Safety and reactogenicity will be assessed by clinical review of all relevant parameters, including solicited ARs (local and systemic ARs), unsolicited AEs (including any clinical safety laboratory abnormalities), treatment-related AEs, severe AEs, SAEs, MAAEs, AEs leading to withdrawal from study participation, AESIs, vital sign measurements, and physical examination findings.

The number and percentage of participants with any solicited local AR or solicited systemic AR during the 7-day follow-up period after the study injection will be summarized. A 2-sided 95% confidence interval (CI) using the Clopper-Pearson method will also be provided for the percentage of participants with any solicited AR.

The number and percentage of participants with unsolicited AEs, treatment-related AEs, severe AEs, SAEs, AESIs, MAAEs, and AEs leading to withdrawal from study participation will be summarized. Unsolicited AEs will be coded according to the MedDRA for AR terminology and presented by MedDRA system organ class and preferred term.

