Solicited ARs will be coded according to the MedDRA for AR terminology. The toxicity grading scale for healthy adult and adolescent volunteers enrolled in preventive vaccine clinical trials will be used in this study with modification for rash, solicited ARs, and vital signs (DHHS 2007b). Unsolicited AEs will be presented by MedDRA system organ class and preferred term.

The number of events of unsolicited AEs/SAEs, AESIs, MAAEs, and AEs leading to withdrawal will be reported in summary tables accordingly. For all other safety parameters, descriptive summary statistics will be provided.

Assessment of safety laboratory tests will be done for this study. The number and percentage of participants who have chemistry and hematology results below or above the normal laboratory ranges will be tabulated by time point. For treatment-emergent safety laboratory test results, the raw values and change from baseline values will be summarized by vaccination group and visit at each time point.

Vital sign results will be presented.

Table 9 summarizes the analysis strategy for safety parameters. For all other safety parameters, descriptive summary statistics will be provided. Further details will be described in the SAP.

Table 9: **Analysis Strategy for Safety Parameters**

Safety Endpoint	Number and Percentage of Participants, Number of Events	95% CI
Any solicited AR (overall and by local, systemic)	X	X
Any unsolicited AE	X	_
Any SAE	X	_
Any unsolicited MAAE	X	_
Any unsolicited AESI	X	_
Any unsolicited treatment-related AE	X	_
Any treatment-related SAE	X	_
Any unsolicited AE leading to withdrawal from study participation	X	-
Any severe unsolicited AE	X	_
Any treatment-related severe unsolicited AE	X	_

Abbreviations: AE = adverse event; AESI = adverse event of special interest; AR = adverse reaction; CI = confidence interval; MAAE = medically attended adverse event; SAE = serious adverse event.

Note: 95% CI using the Clopper-Pearson method. X = results will be provided.

Immunogenicity Analyses 9.5.3.

Immunogenicity analyses will be reported based on the PP Set and provided by vaccination group, unless otherwise specified.

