3 STUDY ENDPOINTS

3.1 Primary Endpoints

Safety

- Frequency and grade of each solicited local and systemic reactogenicity adverse reaction (AR) during a 7-day follow-up period post-vaccination
- Frequency and severity of any unsolicited adverse events (AEs) during the 28-day follow-up period post-vaccination
- Frequency of any serious adverse events (SAEs), adverse events of special interest (AESIs), medically attended adverse events (MAAEs), and AEs leading to withdrawal from Day 1 through Day 181/end of study (EoS)
- Safety laboratory abnormalities through 7 days post-vaccination

Immunogenicity

- Geometric mean titer (GMT) and geometric mean fold rise (GMFR) at Day 29 compared with Day 1 (baseline) and percentage of participants with seroconversion, defined as a Day 29 titer $\geq 1:40$ if baseline is $< 1:10$ or a 4-fold or greater rise if baseline is $\geq 1:10$ in anti-hemagglutinin (HA) antibodies measured by hemagglutination inhibition (HAI) assay
- GMT and GMFR of anti-neuraminidase (NA) measured by neuraminidase inhibition (NAI) assay at Day 1 and Day 29 and percentage of participants with a change in the Day 29 titer of at least 2-/3-/4-fold rise, defined as $\geq 2-/3-/4$ -fold of

the lower limit of quantification (LLOQ) if the Day 1 titer is < LLOQ; or $\geq 2\text{-}3\text{-}4\text{-}$ fold of the Day 1 titer if the Day 1 titer is \geq LLOQ

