7 CHANGES FROM PLANNED ANALYSES IN PROTOCOL

Not applicable.

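### The SAP drops, without declaring it, the protocol's by-arm count of laboratory results outside the normal range, so out-of-range results with no toxicity grade are not counted by arm

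*SAP*

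**What the plan says.** Both documents list the same primary endpoint, which SAP 3.1 words as "Safety laboratory abnormalities through 7 days post-vaccination". Neither attaches a grade or a reference-range threshold to it.

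The planned summaries differ. Protocol 9.5.2, repeated in the synopsis, commits to the number and percentage of "participants who have chemistry and hematology results below or above the normal laboratory ranges will be tabulated by time point". The grouping comes from the opening of the same section: "All safety analyses will be provided by vaccination group".

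SAP 6.4.4 lists four outputs:

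- continuous summaries, in which "the observed values and changes from baseline will be summarized at each time point by vaccination group and then by age group";
- a severe-abnormality table: "Summary of Grade 3+ laboratory abnormalities by visit and toxicity grades will be provided by vaccination group", also by age group;
- a shift table: "Hematology and chemistry toxicity grades will be summarized using a shift table from baseline to Day 8 by vaccination group";
- listings, in which results outside the reference range are flagged and Grade 3 or higher results are listed separately.

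The table of participants below or above the normal range is not among them. SAP section 7, on changes from the protocol's analyses, reads "Not applicable". SAP section 1 gives the SAP precedence where its methods differ from the protocol's.

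**The concern.** The protocol names one categorical summary for a primary safety endpoint, and the document that will be programmed does not contain it. With the SAP taking precedence and declaring no change, the table disappears and a reader of the study report has no notice of it.

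Protocol section 9 requires a protocol amendment if statistical methods tied to the primary objectives change after the study has begun and before unblinding. The documents do not show whether the omission is an oversight or a decision, nor when it was made. Either way the record needs correcting.

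The practical stake is what the remaining tables cannot show. The toxicity scale and the laboratory's reference range are different yardsticks, so a by-arm table built on one does not reproduce a count built on the other. Protocol 2.3.2 reports laboratory abnormalities, including rises in liver tests, with similar mRNA vaccines. In a dose-ranging study it is reasonable to want mild departures from normal counted by dose.

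**Working it through.** The documents give no expected rate for laboratory abnormalities. Their only sample-size figures are the chances of seeing at least one event among 70 participants. These reproduce: 1 - 0.98^70 = 75.7% (stated as 76%) and 1 - 0.96^70 = 94.3% (stated as 94%). The point does not rest on them, so the check is mainly a comparison of text.

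**Step 1: tests and time points.** The Schedule of Events names eight tests: WBC, hemoglobin, platelets, ALT, AST, creatinine, alkaline phosphatase and total bilirubin. Draws are scheduled at Screening and Day 8 only, so Day 8 is the one scheduled post-vaccination look.

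**Step 2: which directions have a grade.** Eight tests, low and high, give 16 directions.

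| Test | Low graded in SAP Appendix E? | High graded? |
|---|---|---|
| WBC | yes | yes |
| Hemoglobin | yes | no |
| Platelets | yes | no |
| ALT | no | yes |
| AST | no | yes |
| Alkaline phosphatase | no | yes |
| Total bilirubin | no | yes |
| Creatinine | no | yes |

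Graded: 2 + 1 + 1 + 5 = 9. Ungraded: 16 - 9 = 7.

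**Step 3: gaps inside the graded directions.** Grade 1 for ALT, AST and alkaline phosphatase starts at 1.1 x ULN, so a value between 1.0 and 1.1 x ULN is abnormal but ungraded. Grade 1 for low platelets covers 125,000 to 140,000, so a count above 140,000 but below the laboratory's lower limit is ungraded. The protocol's own AESI table (Appendix 3) notes platelets below 150 x 10^9, which I read as per litre, or 150,000 per mm3. A count of 145,000 meets that note yet has no toxicity grade.

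**Step 4: where each kind of Day 8 result is counted.**

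| Day 8 result | Grade 3+ table | Shift table | Count outside range, by arm |
|---|---|---|---|
| Grade 3 or 4 | yes | yes | omitted |
| Grade 1 or 2 | no | yes | omitted |
| Out of range, no grade | no | not distinguished from normal | omitted |

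Only the last row has no categorical by-arm laboratory count.

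**Step 5: the overlap is not one-way.** Appendix E also grades any hemoglobin fall from baseline of up to 1.5 as Grade 1. If that row is applied, the shift table will count participants whose values are normal. Neither count can be derived from the other.

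**Step 6: illustrative size (assumption).** Suppose 2.5% of participants fall outside the range in each ungraded direction whatever they receive.

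- Seven independent directions: 1 - 0.975^7 = 16.2%; 70 x 0.162 = 11.4 per arm.
- Complete overlap (always the same participants): 2.5%; 70 x 0.025 = 1.75 per arm.
- No lower limits flagged for the five chemistry tests, leaving only high hemoglobin and high platelets: 1 - 0.975^2 = 4.9%; 70 x 0.049 = 3.5 per arm.

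These are background rates expected in every arm, not vaccine effects, and they exclude the Step 3 gaps.

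**Step 7: age groups.** In SAP 6.4.4 the continuous and Grade 3+ sentences each add a split by age group; the shift-table sentence names vaccination group only. As specified there, Grade 1 and 2 results are not split by age. The general statements in SAP 6.2.9 and 6.4 call for age-group displays, so the split may be intended, but the specific sentence leaves it open.

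**The case against.** The strongest reply is that little clinical information is lost. The shift table has no Grade 3 cut-off, so Grade 1 and 2 results are tabulated by arm. Small liver-test rises also move the continuous summaries. Abnormal values judged clinically significant are recorded as adverse events and enter those tables. Five of the seven ungraded directions are low values of chemistry tests, whereas the concern the protocol names is increases in liver tests, a direction that is graded apart from the 1.0 to 1.1 x ULN gap. The scale in Appendix E is also the one the protocol adopts. Finally, the SAP describes itself as adding to Protocol section 9 and never says the table is withdrawn.

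Most of this stands, and it limits the size of the point. It does not remove it. Means do not give a count of participants, adverse-event reporting depends on investigator judgement, and a SAP that lists its laboratory outputs without this table will be programmed without it.

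Two stronger readings are tempting. A reader might infer that the endpoint was redefined from any out-of-range result to Grade 3 or higher. The documents do not support this: the endpoint is worded identically and without a threshold in both. A reader might also infer that most abnormalities are never tabulated by arm. The shift table contradicts that, and no figure in the documents supports the word most. Setting the share with any out-of-range result (1 - 0.95^8 = 34% for eight independent tests, if each range covers 95%) against a Grade 3+ rate near zero is the wrong comparison, because it leaves the shift table out.

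**Conclusion.** The point holds as an undeclared omission. A protocol-specified summary of a primary safety endpoint is missing from SAP 6.4.4, while SAP section 7 reports no change and SAP section 1 gives the SAP precedence.

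The loss is specific: the by-arm count of out-of-range results with no Appendix E grade, meaning 7 of 16 test directions plus the gaps next to Grade 1. In addition, SAP 6.4.4 specifies no age-group split for Grade 1 and 2 results. How many participants this affects cannot be computed from the documents. The illustration of roughly 2 to 11 of 70 per arm rests on an assumed 2.5% per direction and on how far the directions overlap.

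**What to change.** In SAP 6.4.4, add the protocol's table: number and percentage of participants below and above the normal range, by test, visit (baseline and Day 8), vaccination group and age group. The baseline column matters because exclusion criterion 2 is written in grades, so participants can enter with an out-of-range value that is ungraded or Grade 1. State that the shift table shows all grades, 0 to 4, and present it by age group too. Keep the Grade 3+ table as it is.

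If the sponsor prefers the graded summaries alone, amend Protocol 9.5.2 and declare and justify the change in SAP section 7.

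A further table of new or worsened abnormalities of any grade, with Clopper-Pearson intervals, is not needed to close this point. No document promises one, Protocol Table 9 plans safety intervals only for solicited reactions, and the hemoglobin any-decrease row would inflate it.

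The cost is one or two extra tables from data already collected and already flagged in the listings.

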6.4.5 Vital Sign Measurements

Vital sign measurements, including systolic and diastolic blood pressures (BP), heart rate, respiratory rate, and body temperature, will be presented in a data listing. The values that are outside the reference ranges will be flagged in the data listing. The abnormalities

meeting the toxicity grading criteria (Grade 3 or higher) in [Appendix F](#) in any vital sign measurement will be listed separately.

Observed values and changes from pre-vaccination (baseline) to post-vaccination at Day 1 for all vital sign measurements will be summarized by vaccination group and then by age group as defined in [Section 6.2.9](#).

Shift from baseline in the toxicity grades to post-vaccination result at Day 1 will also be summarized by vaccination group and then by age group.

